10.10. Adjustment of Confidence Intervals and P-values for Multiple Statistical Tests

For the number of comparisons we are conducting, we do not trigger the need for multiple comparison adjustments under the CHI impact evaluation guidance.

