2. PROJECT SUMMARY

2.1. Project Description

The objective of this project is to evaluate the use of personalised budgets as an intervention to: reduce the length of people's experiences of homelessness; reduce the likelihood that homelessness recurs; increase wellbeing and life satisfaction; improve financial security; and secure or maintain employment. The research will consist of a randomised controlled trial, accompanied by an Implementation and Process Evaluation and an economic evaluation.

The intervention is delivered by an organisation called Greater Change in partnership with local homelessness charities in England and is being funded by the Centre for Homelessness Impact (CHI) via the MHCLG-funded Test and Learn / Systems-wide Evaluation Programme. Local homelessness charity partners provide frontline support and refer people to Greater Change in order for them to access financial support.

This project is being conducted as an individually randomised controlled trial, with data collection at baseline, 6 and 12 months post-randomisation, focused on housing stability and perceived housing quality and satisfaction as joint primary outcomes, and financial security, subjective wellbeing, life satisfaction and employment as secondary outcomes. An Implementation and Process Evaluation will interrogate participants' lived experiences of the programme, as well as barriers to and enablers of the project's success. This Implementation and Process Evaluation will consist of a series of semi-structured interviews with participants, focus groups with caseworkers and Greater Change, and analysis of management information from charity partners and Greater Change.

An economic evaluation will consider whether or not the project is cost-effective by considering both the costs per unit of impact and the estimated social return on investment.

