6.4. Trial Flow Diagram

7. OUTCOME MEASURES

7.1. Primary Outcome

Definition

Following the above Theory of Change, we are primarily interested in measuring potential changes in participants' housing outcomes. Our primary outcome measure will therefore be the number of days out of the 360 days after they were randomised that a person is in secure accommodation. This main analysis will be conducted after the endline data collection 12 months after randomisation.

For this purpose, we will be assessing participants' housing stability and their perceived housing quality and satisfaction (see Annexes B and C). We deem it necessary to complement participants' housing history with questions regarding other relevant aspects of housing such as 1) affordability, 2) choice, independence, privacy, 3) suitability.

Instruments

Questions concerning participants' housing history have been adapted from the Residential Time Line Follow Back Inventory (Tsemberis, S. et al. (2007; see Annex B). Modifications have been mainly made to simplify and adapt the questions to the UK context. Similarly, minor modifications have been made to the OMRA tool, which includes questions about general satisfaction with housing, affordability, choice, independence, and privacy, and suitability.

When is it measured

Participants' data used in this analysis will be collected at three time points: baseline (prior to randomisation) and endline (12 months after randomisation). We will also collect these measures at 6 months after randomisation, and this will be included in our interim analyses.

 For whom is it measured All participants in the treatment and control groups will be surveyed by IFF.

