9. SAMPLE SIZE AND POWER CALCULATION

9.1. Sample Size / Power Calculation

Sample size is limited by the availability of funding to deliver the personalised budgets. We therefore provide the power implications of various attrition scenarios between baseline and a single endline (i.e. the 12-month follow-up).

Under our likely attrition scenario of 25%, our minimum detectable effect size (MDES) at alpha = 0.05 and beta = 0.8 is 0.273, representing a moderate effect size. Owing to the costly nature of the intervention and effect sizes observed in similar studies, we believe this is acceptable.

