9.2. Attrition Assumptions

We have assumed a 25% attrition between baseline and endline data collection, as this is similar to the current attrition rate on a similar cash transfer trial conducted by King's College London. This has the effect of reducing the effective sample size to 270 participants and increasing the MDES by 15%. Scenario C in the table below also provides calculations for a more conservative sample with 35% attrition, which leads to a further increase of the MDES to 0.293. However, even with this higher attrition rate, we judge the sample size to be sufficient to detect a relevant effect size given the magnitude of the intervention.

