9.3. Software

Power calculations were carried out in the statistical software R.

Table 7: Sample size calculations

	Scenario A	Scenario B	Scenario C
Minimum Detectable Effect Size (MDES)	0.236	0.273	0.293

Pre-test/ post-test correlations	level 1 (participant)	0.6	0.6	0.6
	Alpha	0.05	0.05	0.05
	Power		0.8	0.8
Alternative hypothesis: One-sided or two-sided		Two-sided	Two-Sided	Two-Sided
	Intervention	180	180	180
Number of participants	Control	180	180	180
	Total	360	360	360
Expected attrition at individual level	%	0	25	35
Effective sample (Participants)	Total	360	270	234

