10.3. Primary Analyses

Analytical approach

Our main analytical approach for our primary analysis is regression analysis, which will be conducted on an intention-to-treat, complete cases basis. For our main housing outcomes, housing stability and perceived housing quality and satisfaction, measured via Residential Time Line Follow Back Inventory and the OMRA tool, we will conduct a linear regression, evaluated at the mean. Formally, this will be an autoregressive (AR-1), model, specified as:

$$Y_{ipt} = \alpha + \beta_1 Y_{ip0} + \beta_2 B_i + \beta_3 X_i + \beta_4 P_p + u_i$$

Where:

 Y_{ipt} is the value of the respective outcome measure (housing stability and perceived housing quality and satisfaction), for participant i at time t (endline in the primary analysis), referred by charity partner p.

 α is a regression constant

 Y_{i0} is the baseline value of the outcome for participant i in charity partner p.

 B_i is a binary treatment indicator set to 1 if participants are treated and zero else.

 X_i is a vector of participant demographic characteristics including gender (operationalised as a trinary variable) and age (operationalised as a categorical variable with 7 values including prefer not to say).

 P_p is a vector of charity partner fixed effects, reflecting that charity partner is a stratification variable.

 u_i is an error term.

This analysis will be conducted with two values of the time indicator, at the midline and endline data collection points, in both cases using the baseline data at time 0 as a control. Uncertainty will be reported through confidence intervals at p-values. We will report the binary indicator of whether the treatment effect is statistically significant, as well as present the p-value continuously and the confidence intervals.

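### The protocol gives both one and two primary outcomes, with no success rule and no adjustment; with two, no reading delivers both 5% error and 80% power at 0.273

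*Protocol*

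**What the plan says.** The number of primary outcomes differs between sections.

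- **Two.** Section 2.1 describes the trial as "focused on housing stability and perceived housing quality and satisfaction as joint primary outcomes". Table 1 and section 4.1 also list two. The primary hypothesis in section 5.1 names both, joined by the word *and*. Section 10.3 fits the primary regression to each.
- **One.** Section 7.1 states: "Our primary outcome measure will therefore be the number of days out of the 360 days after they were randomised" in secure accommodation. Section 10.6 repeats that single measure for the main analyses. Section 7.1 goes on to say that both housing stability and perceived quality are assessed to this end, but it does not define the second as an endpoint.

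Section 10.3 reports a significant or not significant verdict beside the p-value and confidence interval. It also runs the model at two times: "This analysis will be conducted with two values of the time indicator, at the midline and endline data collection points". The same section and section 7.1 make endline the primary time point.

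Section 10.10 settles multiplicity by reference to the funder's guidance: "For the number of comparisons we are conducting, we do not trigger the need for multiple comparison adjustments under the CHI impact evaluation guidance". It does not say how many comparisons were counted.

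Section 9.1 gives power for one comparison: "our minimum detectable effect size (MDES) at alpha = 0.05 and beta = 0.8 is 0.273". The 0.8 written as beta there is labelled power in Table 7.

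**The concern.** A primary analysis needs a fixed number of primary tests and a rule for turning their results into a conclusion. This protocol has two counts and no rule. Section 10.10 is a positive decision against adjustment, so a later analysis plan could not add one without contradicting the protocol.

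The practical risk is a split result. Suppose days in secure accommodation show no significant effect and the satisfaction score does. Under sections 2.1 and 10.3 this could be reported as success on a primary outcome. Under sections 7.1 and 10.6 the primary outcome failed. If both outcomes were needed, the primary hypothesis failed as well. The choice would be made after the results are known.

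Participants know their allocation (sections 4.1 and 5.2); section 5.4 masks only outcome assessors and analysts. The satisfaction items in Annex C ask directly how people feel about their housing, so the success rule decides how much weight such a rating carries.

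**Working it through.** **Inputs.** Two-sided alpha 0.05, power 0.80 and pre/post correlation 0.6 (Table 7). 360 randomised 1:1 (section 5.2, Table 7). 270 analysed at 25% attrition and 234 at 35% (section 9.2, Table 7). The correlation between the two outcomes' test statistics is not given; I assume a range of 0 to 0.9.

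**Step 1: reproduce the plan's figure.** MDES = (z for alpha + z for power) × √(1 − 0.6²) × √(4/N), with √(1 − 0.36) = 0.8 and 1.9600 + 0.8416 = 2.8016.

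- N = 360: 2.8016 × 0.8 × √(4/360) = 0.236
- N = 270: 2.8016 × 0.8 × √(4/270) = 0.273
- N = 234: 2.8016 × 0.8 × √(4/234) = 0.293

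All three match Table 7, including the 35% case, "which leads to a further increase of the MDES to 0.293". The arithmetic is correct for one primary test.

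**Step 2: two outcomes, either suffices, each at 0.05.** Family-wise error = 1 − P(|Z₁| < 1.96 and |Z₂| < 1.96). At zero correlation this is 1 − 0.95² = 0.0975. Other values come from the bivariate normal.

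**Step 3: two outcomes, both required, each at 0.05.** The error rate is at most 5%, because a false claim needs rejection of at least one true null hypothesis. If both null hypotheses are true and the tests independent it is 0.05² = 0.25%. Joint power with a true effect of 0.273 on each outcome = 0.80 + 0.80 − P(at least one significant). At zero correlation this is 0.80² = 0.64.

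| Correlation | Family-wise error, either | Power for at least one | Power for both |
|---|---|---|---|
| 0 | 9.75% | 96% | 64% |
| 0.3 | 9.5% | 93% | 67% |
| 0.5 | 9.1% | 91% | 69% |
| 0.7 | 8.3% | 89% | 71% |
| 0.8 | 7.8% | 87% | 73% |
| 0.9 | 7.0% | 85% | 75% |

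**Step 4: what each repair does to the MDES at N = 270.**

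- One primary outcome: 0.273, unchanged.
- Bonferroni, 0.025 per outcome: (2.241 + 0.842) × 0.8 × √(4/270) = 0.300. Power per outcome at 0.273 is then 71.3%. Restoring 80% at 0.273 would need 328 analysed, or 328/0.75 ≈ 438 randomised.
- Holm: at most 0.300, since Holm never has less power per outcome than Bonferroni.
- Both required, 80% joint power: 0.313 at correlation 0, 0.305 at 0.5 and 0.295 at 0.8.

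**The case against.** **The error and the power are not both lost.** A reader might infer that both the 5% and the 80% fail. The documents do not support that. Under an either rule only the error rate suffers: the chance of at least one success is 85% to 96% if both effects equal 0.273, and at least 80% if only one does. Under a both rule only the power suffers. Under the single primary of section 7.1 both figures hold. This stands.

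**Midline should not be counted.** Two outcomes at two times make four tests, and 1 − 0.95⁴ = 18.5%. It is tempting to quote this. But sections 7.1 and 10.3 make endline primary, and sections 7.1 and 10.8 treat the six-month results as interim. The 360-day measure also contains the first 180 days (section 10.6), so independence would be a poor assumption. The figure is not part of this point.

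**The text leans towards both.** Section 5.1 joins the outcomes with *and*, and section 2.1 calls them joint. If that is the intention, error is controlled. But neither section states a decision rule, and the power then falls below the stated 80%.

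**Section 10.10 follows outside guidance, and p-values and intervals will be shown.** The guidance is not in the documents, so whether its threshold is met cannot be judged. Readers could apply a correction themselves. Neither fact settles which outcome carries the conclusion, and a guidance threshold does not alter the error rate under an either rule.

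**Both outcomes are unblinded self-report.** Annex B collects housing dates as best guesses from the same participants. Satisfaction is the more subjective of the two, but the contrast is one of degree, and the point does not depend on it.

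**Conclusion.** The point holds. The protocol contradicts itself on the number of primary outcomes, sets no rule for combining them, and declines adjustment. With two primaries each tested at 0.05, an either rule puts family-wise error at about 7.0% to 9.75%, and a both rule puts joint power at about 64% to 75%. Neither reading gives 5% and 80% together at 0.273.

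These ranges rest on an assumed correlation of 0 to 0.9 between the test statistics; the shortfall would vanish only as the two tests became perfectly correlated. The joint power also assumes a true effect of 0.273 on each outcome and the plan's 0.6 pre/post correlation for both.

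The 0.273 should not be called wrong: it is right for the single primary test that sections 7.1 and 10.6 describe. The matter should be settled before the endline analysis, because it determines what the trial may conclude.

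**What to change.** **Preferred.** Name days in secure accommodation over the 360 days after randomisation, analysed at endline, as the sole primary outcome, as sections 7.1 and 10.6 already do. Make perceived housing quality and satisfaction the first secondary outcome. Align Table 1 and sections 2.1, 4.1, 5.1, 10.3 and 10.10. The 5%, 80% and 0.273 then stand without recalculation.

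**If both stay primary.** Amend section 7.1 to say so, and state one rule in section 10.10:

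- Holm across the two endline tests, with the MDES at N = 270 given as at most 0.300; or
- both must be significant at 0.05, with joint power of about 64% to 75% at 0.273 stated with its correlation assumption.

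Restate section 9 and Table 7 to match the rule chosen.

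**Cost.** No new data or participants are needed. Either one outcome loses primary status, or the stated MDES or power becomes less favourable. It is more than a wording change: version 2.0 is dated 17 June 2025, and Table 4 places midline collection in February to June 2025 and the interim report in July 2025. The change should therefore go into a dated, justified addendum before endline analysis, by the route in section 13.2, stating whether midline results by arm had been seen.

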11. IMPLEMENTATION AND PROCESS EVALUATION (IPE)

11.1. Aims, Objectives and Research Questions

The objectives of this Implementation and Process Evaluation emerge from the Theory of Change of the intervention described previously and aim to test overall participants' and other stakeholders' responses to and feelings about the intervention, as well as questions of fidelity and compliance. These research questions follow in large part those asked in previous, similar, cash transfer trials.

Aims

 To understand what participants thought about the personalised budget they received, how they intended to spend it, how it was actually spent, and why;

- To identify factors that helped or hindered participants' spending of the personalised budget in ways that they considered to enable them to advance their own goals and aspirations;
- 3. To understand better the extent to which poverty is alleviated by the intervention
- To explore the perceptions of staff and stakeholders regarding the opportunities and risks of providing financial assistance in this form;
- 5. To gather feedback from participants and stakeholders about how the benefits of personalised budgets could be maximised;
- To explore the readiness of the Greater Change personalised budgets model for wider roll-out, scaling or further evaluation, considering the extent to which fidelity was adhered to in screening and budget planning processes.

• Research Questions

Fidelity

- 1. Was the intervention delivered in the way it was intended?
 - How closely are the caseworkers adhering to the guidelines and procedures outlined by Greater Change?
- 2. How effective were the deliberative processes between participants, their support workers and Greater Change on how to decide the purpose of the personalised budget perceived to be?
 - To what extent were recipients actively engaged in the planning and utilisation of their personalised budgets, and what factors influenced their level of engagement?
- 3. Did caseworkers feel well-positioned to support participants who were assigned a personalised budget?
- 4. To what extent did caseworkers feel able to screen participants according to the criteria provided, administer the personalised budget, and support participants to consider how to spend it following the guidelines provided by Greater Change?

Risks and opportunities

- 5. What were the key opportunities and risks identified by staff and stakeholders?
- 6. What were the key facilitators and barriers to participants using the personalised budget to further their own aspirations and goals?

Participants' experiences and outcomes

- 7. How would participants describe their current housing situation, how has it changed since they joined the evaluation, and what are their feelings about it?
- 8. How would participants describe their current financial situation, how has it changed since they joined the evaluation, and what are their feelings about it?
- 9. What are the participants' perspectives on the future and their aspirations?

For treatment participants specifically:

- 10. What were participants' experiences of being assigned a personalised budget?
- 11. How did they spend it and why? Did the budget change their other spending?
- 12. How and to what extent did recipients feel that the personalised budgets affected their lives?
- 13. Have recipients experienced any changes in other areas of their lives not covered by the listed primary and secondary outcomes? (e.g. substance use, gambling, social relationships and community integration, access to support services, criminal justice involvement,...)
- 14. How did receiving a personalised budget influence the way participants thought about themselves and their future prospects?

For control participants specifically:

- 15. Are there adverse outcomes or experiences for people assigned to the control groups?
- 16. What were their thoughts regarding the received signposting to financial resources?

Future improvements

- 17. How can the experiences of people who have received the personalised budget inform our understanding of the effectiveness and accessibility of this type of financial assistance?
- 18. What are staff and stakeholders' recommendations for improvement, and perceptions of the readiness of this form of financial assistance for rollout and scaling?

11.2. Research Design and Methods

For the Implementation and Process Evaluation we will be making use of three methods to answer the research questions specified above. Semi-structured interviews with participants in the treatment and control groups to understand the participant experience of the programme; focus

groups with staff at charity partners and Greater Change (focused on understanding their perspective on the participant experience, the process of being part of the programme, and areas for improvement); and analysis of management information from charity partners and Greater Change to understand how much money is allocated, what it is spent on, and when and whether it is spent. Frontline workers were selected for inclusion because they have the best-combined view of both internal processes within their own organisations and the relationship between the project and senior leadership or administration such as finance teams.

Semi-Structured Interviews with Participants

Methodology

Semi-structured interviews: a sub-sample of 20 participants across the treatment and control groups will be invited to take part in an in-depth phone interview. A detailed interview guide will be developed in order to provide structure and ensure consistency across interviews, although the interview will be participant-led and will include multiple opportunities for participants to share what matters to them. In the interview, we will explore aspects of the program's fidelity (i.e. participants' perception of how well integrated they were in the planning conversation), risks and opportunities from the participants' perspective, their experiences and outcomes during the trial period as well as their recommendations for future improvements. This will cover themes such as:

- Participants' future planning and goals, and their feelings about and aspirations for the future;
- Participants' personal (particularly housing and financial) situation and feelings about their current situation;
- How helpful or otherwise the financial/budgeting advice received has been;
- What services do they consider have been particularly helpful (or unhelpful) for their housing and financial situation, and why.

For participants in the treatment group, additional questions will be asked about:

- Their feelings on being informed that they were going to receive the personalised budget support, and any hopes or concerns it brought about;
- What, if any, impact the personalised budget (and what it was spent on) has had on their lives;
- The key facilitators and barriers to using the personalised budget to further their wellbeing, aspirations, goals and sense of autonomy;
- Their experience of the support provided by the delivery organisation during the intervention, particularly how helpful or otherwise the financial/budgeting advice received has been (if engaged with);
- Whether they have any advice on providing additional financial assistance in the most useful way.

 Target population
 We will interview a sub-sample of treatment and control group participants.

Sampling strategy

We will initially interview 5 participants drawn from the treatment group and 5 from the control group. We will then review the data and decide how to sample the remaining 10 interviews. This will allow us to incorporate the voice of control participants in the study, but also to be responsive if interviews with control participants are not providing rich data. We will seek to recruit a sample that represents the diversity of study participants, including minimum quotas on demographic characteristics (e.g. age, gender, and ethnicity). Broad similarity in the sample characteristics across both the treatment and control groups will be sought.

Recruitment

Applicants will be sent an email invitation and/or text message to attend a telephone interview concerning their aspirations and financial situation and (if they are in the treatment group) the personalised budget. Applicants are not required to participate in the interviews, and consent to be interviewed will be sought separately from consent to participate in the trial. During the data collection process, consent will be treated as an ongoing process, reiterating that participants are able to withdraw their consent at any point. A reminder will be sent the day before the scheduled interview to minimise sample attrition.

We will collaborate with caseworkers in the charity partners, who will be briefed and provided with inclusion/exclusion criteria to aid this process.

Participants will be compensated with a £35 digital voucher per interview and a maximum of one interview per participation.

Data collection data sources

Data will be collected from the semi-structured interviews with selected participants. A detailed interview guide will be developed in order to provide structure and ensure consistency across interviews.

Data collection procedures

Interviews will be conducted by trained and experienced researchers, following the risk and safeguarding protocol (see Annex G) for the present study. Interviews will be conducted by phone or videoconferencing, according to the interviewee's preference. Interviews will be audio-recorded and transcribed; however, names will not be transcribed.

Data quality, assurance and confidentiality
 All audio recordings will be stored securely and destroyed following
 transcription. All personal information will be removed from
 transcripts, and transcripts will be stored using the participant's
 pseudonymous identifier to link them to the survey responses and
 demographics of the participant. All transcripts will be stored securely,

and access will be limited to the research team of the present study only.

Focus groups with caseworkers and Greater Change

Methodology

We will conduct four focus groups with staff at the charity partners involved in working with participants, as well as with Greater Change staff responsible for the intervention. Each focus group will consist of 4-5 participants. A focus group topic guide will be facilitator-led and developed in order to provide structure and ensure consistency across focus groups, although the groups will be participant-centred and will include multiple opportunities for participants to share what matters to them. In the focus groups, we will predominantly explore themes concerning the program's fidelity, risks and opportunities provided by administering personalised budgets, and their recommendations for improvements to the intervention::

- These stakeholders' impressions of how smoothly the personalised budgets process has run (e.g. whether caseworkers perceived themselves to be well instructed for the purposes of screening and planning of the personalised budgets and able to follow the provided guidelines)
- Their feelings about the appropriateness of the level and type of support provided through the personalised budgets.
- What they felt were the opportunities and risks of giving personalised budgets in this way, and the perceived changes in participants' outcomes.
- Their impression of control group participants' experiences of not being assigned a personalised budget.
- Whether the deliberative process between charity partners,
 Greater Change and participants was thought to be effective and efficient, based on the instructions provided.
- Recommendations for improvements to the service.

Target population

We will recruit participants for focus groups who are caseworkers working in charity partners and staff at Greater Change.

Sampling strategy

We will initially construct two focus groups. The first will consist of caseworkers solely at charity partners around the country. The second will consist of a mix of caseworkers and employees of Greater Change. We will aim to get a diverse pool of caseworkers from different organisations at this stage, but we will not include managers of other senior leaders in the focus groups. We will sample in this way because we believe that involving managers would change the power dynamic of the groups, and because we believe that frontline workers, who work as an interface between the participants and the wider processes and leadership of the charity partners, have the more comprehensive set of perspectives. After conducting these focus groups, we will decide whether the quality of the information is higher

when Greater Change employees are present, or not, and use this to inform our strategy. Through regular conversations with Greater Change, we will monitor whether there is particularly strong, or particularly weak, delivery in some places, and may seek to oversample those areas.

Recruitment

We will request details of all caseworkers working on this trial from charity partners, as well as all Greater Change staff working on the trial. We will then sample participants based on the process above, contact the charity partners to let them know who we have selected and provide a variety of times when a focus group could take place. Once enough selected participants have agreed to a particular time, and have completed an online consent form, we will schedule the focus group.

- Data collection data sources
 Data will be collected from the focus groups with selected stakeholders. A topic guide to structure the discussion will be developed in order to provide structure and ensure consistency across focus groups.
- Data collection procedures
 Focus groups will be conducted by trained and experienced researchers, following the risk and safeguarding protocol for the present study. Focus groups will be conducted by videoconferencing or in person depending on the group's makeup and location. Focus groups will be audio-recorded and transcribed; however, names will not be transcribed.
- Data quality, assurance and confidentiality
 All audio recordings will be stored securely and destroyed following
 transcription. All personal information will be removed from
 transcripts, and transcripts will be stored using the group's
 pseudonymous identifier to link them to the survey responses and
 demographics of the participants. All transcripts will be stored
 securely, and access will be limited to the research team of the
 present study only.

Administrative data from Greater Change and Charity Partners

- Data collection data sources
 We will collect quantitative data from Greater Change and charity partners relating to:
 - The dates on which participants are randomised; funding is agreed, sent to charity partners; and spent by charity partners.
 - The amounts of money being disbursed.
 - What funding is spent on.
 - For the control group, any information held by charity partners on other financial support that they have received (to facilitate dose-response analysis).
- Data collection procedures

Every two months during participant recruitment, we will send a template to each charity partner and to Greater Change with a list of participants assigned to the treatment and control group with their unique identifiers, and ask them to complete the fields for every participant. The researcher assigned to this procedure will not be involved with the final analysis to ensure no bias is introduced.

